Attachment 1

Study Protocol

(Version number: V4.0 Version Date: 2022/04/28)

Project Name : A novel SaCoVLM™ video laryngeal mask
airway in airway management for morbidly obese patients in
bariatric surgery: a single-arm prospective study

Project source: Researchers initiated

Department responsible: Anesthesia and Postoperative Medicine
Department

Principal Investigator: [name]

A novel SaCoVLM™ video laryngeal mask airway in airway management for morbidly obese patients in bariatric surgery: a single-arm prospective study

Abstract

Objective: The SaCoVLM™ video laryngeal mask is a novel video-assisted device that integrates the functions of both a dual-channel laryngeal mask airway (LMA) and an intubating laryngeal mask airway (ILMA). Theoretically, it can provide reliable awake airway management for obese patients undergoing laparoscopic sleeve gastrectomy (LSG). **Methods:** This single-arm prospective study evaluated the efficacy and safety of the SaCoVLM™ video laryngeal mask airway in 57 morbidly obese patients (BMI ≥ 35 kg/m²) undergoing LSG.

Keywords: Video laryngeal mask airway; Morbidly obese patients; Airway management; Laparoscopic sleeve gastrectomy; First-attempt success rate.

Background

With rapid social and economic development, the dietary environment and lifestyles of residents have undergone tremendous changes, resulting in a steady increase in the prevalence of overweight and obesity [1]. However, in morbidly obese patients, the long-term results of lifestyle management and medication regimens with poor adherence are unsatisfactory [2]. Twelve previous randomized clinical trials have found surgery to be significantly more effective than medication for weight control in morbidly obese patients [3]. Laparoscopic sleeve gastrectomy (LSG) has become one of the mainstream bariatric surgeries globally due to its simple operation and minimal impact on the physiological structure of the digestive tract [4]. Unfortunately, airway management in morbidly obese patients remains a critical challenge in clinical practice due to anatomical and physiological alterations, such as increased neck circumference, reduced pharyngeal space, and decreased functional residual capacity [5]. These factors contribute to a higher incidence of difficult mask ventilation,

difficult intubation, and perioperative respiratory complications, posing significant risks to patient safety [6-8].

Conventional supraglottic airway devices, while widely used, may exhibit limitations in achieving optimal airway sealing pressure or providing reliable visualization during placement, particularly in patients with a high body mass index (BMI) [9, 10]. Recent advancements in airway technology, such as video laryngeal mask airways (VLMs), offer potential solutions by combining the benefits of supraglottic ventilation with real-time visual guidance, potentially enhancing first-attempt success rates and minimizing airway manipulation. The SaCoVLM™, a novel video LMA, integrates a high-resolution camera into its design, enabling direct visualization of the glottis during insertion and positioning [11]. Since 2022, several studies have reported that SaCoVLM™ allows partial or complete visualization of the laryngeal inlet and has the advantages of high success rate, high sealing pressure and smooth gastroesophageal drainage [11-14]. SaCoVLM™ is currently being used in many types of patients, including adult patients with normal BMI [12], children with microtia [13], patients with lateral decubitus surgery [14] and others. However, despite growing interest in video-assisted airway devices, evidence regarding their efficacy and safety in morbidly obese populations remains sparse. This single-arm prospective study aims to evaluate the feasibility, performance, and clinical outcomes of the SaCoVLM™ in airway management for morbidly obese patients undergoing LSG. By systematically video LMA analyzing first-attempt success rates and adverse events such as aspiration or airway trauma et al., this investigation directly addresses the relationship between obesity-related features and SaCoVLM™ advantages. Furthermore, the study will correlate intraoperative airway metrics with postoperative respiratory complications, a critical yet understudied linkage in bariatric surgery

outcomes. In summary, this study will contribute critical data to guide device selection and optimize perioperative care in this high-risk cohort.

Materials and methods

Trial design

This single-arm prospective study was conducted at the University-affiliated hospital to evaluate the efficacy of a novel SaCoVLM™ in airway management for morbidly obese patients. The details of the video laryngeal mask are as previously described by us (Figure 1) [14]. The study protocol received committee of the First Affiliated Hospital of Shandong First Medical University & Shandong Provincial Qianfoshan Hospital (Approval number: YXLL-KY-2022 035). Prior to any screening or study procedures, written informed consent was obtained from all participating patients. The research was conducted in strict accordance with Good Clinical Practice guidelines, International Council for Harmonisation of Technical Requirements for Pharmaceuticals for Human Use standards, ethical principles outlined in the Declaration of Helsinki, and all relevant regulatory requirements.

[figure not shown]

Figure 1. SaCoVLM™ video intubating laryngeal mask airway. Photo courtesy of Zhejiang UE Medical Corp (Hangzhou, China).

2.1 Participants

The study population comprised adult patients aged over 18 years diagnosed with morbid obesity, which was clinically defined as either a body mass index (BMI) ≥ 40 kg/m² or a BMI ≥ 35 kg/m² accompanied by at least one significant obesity-related comorbidity [15]. Eligible participants were required to have no known or suspected difficult airway, demonstrate tolerance for laparoscopic surgery and anesthesia, and be scheduled exclusively for LSG without concurrent additional procedures.

Anesthesia procedures

All anesthesiologists in this study underwent centralized training prior to trial initiation, with documented certification in protocol-specific procedures. No preoperative medications were administered to any patients. Upon entering the operating room, patients were positioned in a semi-fowler position, with intravenous access established. Standard monitoring protocols were implemented, including electrocardiography (ECG), heart rate (HR), non-invasive blood pressure (NIBP), pulse oximetry (SpO₂), end-tidal carbon dioxide (EtCO₂), and bispectral index (BIS), alongside radial artery catheterization for invasive blood pressure monitoring. All patients underwent awake insertion of the SaCoVLM™, with surgery completed under general anesthesia combining the video laryngeal mask and endotracheal intubation.

Immediately upon arrival in the operating room, patients were instructed to hold 10 mL of dyclonine mucilage orally for approximately 10 minutes to achieve topical anesthesia. Premedication included midazolam 2 mg and atropine 0.4 mg, followed by bilateral ultrasound-guided superior laryngeal nerve block using 0.375% ropivacaine. A properly sized laryngeal mask was selected, and under awake conditions, patients

were instructed to open their mouths to facilitate SaCoVLM™. Optimal positioning was confirmed by visualization of complete glottic structures on the monitor screen. The glottic exposure grade was as we previously described (Figure 2) [11, 14, 16, 17]. The cuff was inflated using a handheld manometer, and the mask was connected to the anesthesia machine. Clear glottic visualization on the monitor and the presence of a regular EtCO₂ waveform confirmed proper mask alignment, after which rapid anesthesia induction was initiated.

Grade I Full view of the glottis

Grade II Full view of all laryngeal inlet and posterior glottis

Grade III View includes dark areas indicating an open space:
 (a) No view of the glottis, part of laryngeal inlet
 (b) View to arytenoids, glottis or epiglottis is blurred because of excess light, poor focus, secretions or lubricant

Grade IV No part of the larynx can be identified:
 (a) View of arytenoids, glottis or epiglottis cannot be identified because the LMA is deep
 (b) No part of the larynx can be identified because there are more secretions

Figure 2. Glottic exposure grades. (Based on the suggestions of Timmermann A et. al.)

If suboptimal positioning occurred, the up-down maneuver, cricoid pressure, cuff pressure adjustment, fiberoptic bronchoscopy-guided intubation were applied for

minor adjustments. Under direct video guidance, the endotracheal tube was gently advanced along the natural curvature of the airway. Successful intubation was defined by unimpeded tube passage, direct visualization of tracheal entry, and sustained EtCO₂ waveform. Following intubation, the breathing circuit was immediately connected, and bilateral lung auscultation confirmed symmetrical breath sounds before securing both the mask and endotracheal tube. Intraoperative fluid administration and vasoactive medications were adjusted based on vital signs, urine output, and physiological requirements.

Postoperatively, the endotracheal tube was removed under deep anesthesia, and the video laryngeal mask was retained for transfer to the post-anesthesia care unit (PACU). The laryngeal mask was removed only after patients regained adequate spontaneous respiration, demonstrated responsiveness to verbal commands, and met established extubation criteria.

Outcomes and measures

The primary endpoints of this study were the first-time success rate of intubation after insertion of SaCoVLM™ and the duration of intubation. Secondary endpoints included the time to SaCoVLM™ insertion, the number of attempted insertions, the Endoscopic View Grading System of Laryngoscopic View (EVGS) classification, airway seal pressure, the airway optimization protocol used, postoperative sore throat (POST), postoperative hoarseness, and adverse events consistently detected throughout the study to assess safety.

Statistical analysis

The primary endpoint of this study was the first success rate of intubation after LMA insertion. As previously reported, the assumed first success rate for intubation after standard laryngeal mask insertion is 0.75 [18]. If we assume that the expected success

rate with the SaCoVLM™ is increased to 0.9, with a set level of significance ($\alpha=0.05$, one-sided test), and statistical efficacy ($1-\beta=0.8$), the minimum number of participants required to reject the original hypothesis is at least 42. The final inclusion of 58 participants in this study meets the sample size requirement.

First-attempt intubation success rate was analyzed using an exact binomial test, with the null hypothesis defined as a success rate $\leq 75\%$ and the alternative hypothesis as a success rate $\geq 90\%$, under a one-tailed significance threshold of $\alpha=0.05$. For secondary outcomes, continuous variables (e.g., intubation time, SaCoVLM™ insertion time) are presented as mean \pm standard deviation (SD) and median (range), while categorical variables (e.g., EVGS classification, POST) are reported as counts and proportions. Spearman and Pearson correlation coefficients were used to assess the correlation of variables such as BMI, neck circumference, and OSA severity with the number of intubations attempts and intubation time. Statistical significance was defined as $p < 0.05$. All statistical analyses were performed using IBM SPSS Statistics version 26.0 (IBM Corporation, Armonk, NY, USA), and graphical visualizations were generated with GraphPad Prism version 9.0 (GraphPad Software, San Diego, CA, USA).

Acknowledgments

We would like to thank the staff at the Center for Big Data Research in Health and Medicine, The First Affiliated Hospital of Shandong First Medical University & Shandong Provincial Qianfoshan Hospital, for their valuable contribution.

Institutional Review Board Statement

The study was conducted in accordance with the principles of the Declaration of Helsinki and was approved by the Ethics Review Committee of the First Affiliated Hospital of Shandong First Medical University & Shandong Provincial Qianfoshan Hospital (Approval number: YXLL-KY-2022 035). Written informed consent was

obtained from all individual participants involved in the study prior to any study procedures.

Funding Statement

The research was funded by the Clinical research Special Fund of Wu Jie-ping Medical Foundation (320.6750.2024-15-19), Beijing Health Alliance Charitable Foundation (KM-20240612), and Education and Teaching reform Research project of Shandong First Medical University (Shandong Academy of Medical Sciences) (XM2024091).

Author Contribution

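### The success definition does not exclude a bronchoscope-guided first tube pass, so such cases can be counted as SaCoVLM first-attempt successes and may inflate the primary rate

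*Combined protocol and SAP*

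**What the plan says.** Under Anesthesia procedures, the plan gives a list of measures for a suboptimal mask position: "the up-down maneuver, cricoid pressure, cuff pressure adjustment, fiberoptic bronchoscopy-guided intubation were applied for". It labels all of them as minor. The bronchoscope is thus grouped with three positioning manoeuvres. The sentence after the list describes advancing the tube under video; the text there reads "minor adjustments. Under direct video guidance, the endotracheal tube was gently advanced along the natural curvature of the airway".

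The same section gives the criterion: "Successful intubation was defined by unimpeded tube passage, direct visualization of tracheal entry, and sustained EtCO₂ waveform". It does not mention the bronchoscope or say which device must supply the view.

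Outcomes and measures states: "The primary endpoints of this study were the first-time success rate of intubation after insertion of SaCoVLM™ and the duration of intubation". The Statistical analysis section calls the same quantity the first-attempt rate. Neither term is defined. Among the secondary endpoints is "the airway optimization protocol used", with no link to the primary numerator.

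The benchmark is that "the assumed first success rate for intubation after standard laryngeal mask insertion is 0.75", and the design assumes that the "rate with the SaCoVLM™ is increased to 0.9". The planned test is a one-sided exact binomial at 0.05.

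**The concern.** The up-down manoeuvre, cricoid pressure and cuff adjustment change how the mask sits. Bronchoscope guidance is different in kind, because it supplies a separate view for the tube pass itself. The Background presents the integrated camera as the distinguishing feature of the SaCoVLM. A first pass guided by a bronchoscope can meet all three success criteria, and nothing in the plan says whether it is a success, a failure or a second attempt.

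The trial has one arm and a fixed reference rate, so no concurrent control is scored by the same lenient rule. If assisted passes enter the numerator, they can only raise the rate credited to the device alone. The primary result would then depend on a coding decision that the plan does not state.

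**Working it through.** **Inputs.** From Statistical analysis: null rate p0 = 0.75, expected rate p1 = 0.90, one-sided alpha 0.05, power 0.80, stated minimum 42, enrolled 58. The abstract gives 57 enrolled, so both sizes are shown. The documents give no rate of bronchoscope use. The share of unaided failures that it converts is therefore an assumption, shown from 0% to 50%.

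**The plan's own figure.** With the normal approximation,

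n = [z(0.95)·√(p0(1−p0)) + z(0.80)·√(p1(1−p1))]² / (p1−p0)²
= [1.645 × 0.4330 + 0.8416 × 0.3000]² / 0.15² = 41.36, rounded up to 42.

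The stated minimum reproduces, so p0, p1 and alpha are being read as the plan intends.

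**Rejection limits.** The exact p-value for k successes is P(X ≥ k) with X ~ Bin(n, 0.75).

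- n = 58: 49 successes give p = 0.060 and 50 give p = 0.029. Rejection needs at least 50. Power at 0.90 is 0.879.
- n = 57: 48 give p = 0.068 and 49 give p = 0.034. Rejection needs at least 49. Power at 0.90 is 0.888.

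**Recoding from a result near the planned 90%.** Move assisted cases from success to non-success:

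| Recoded | n = 58 | p | n = 57 | p |
|---|---|---|---|---|
| 0 | 52/58 | 0.0046 | 51/57 | 0.0055 |
| 1 | 51/58 | 0.012 | 50/57 | 0.015 |
| 2 | 50/58 | 0.029 | 49/57 | 0.034 |
| 3 | 49/58 | 0.060 | 48/57 | 0.068 |

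Three cases remove significance at either size.

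**Effect on type I error.** Suppose that unaided first-pass success is truly 0.75, and that a share f of the failures is converted by the bronchoscope and counted as success. The counted rate is 0.75 + 0.25f. The chance of rejection is P(X ≥ 50) at n = 58, or P(X ≥ 49) at n = 57, evaluated at that rate.

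| Assumed f | Counted rate | n = 58 | n = 57 |
|---|---|---|---|
| 0% | 0.750 | 0.029 | 0.034 |
| 5% | 0.763 | 0.046 | 0.053 |
| 10% | 0.775 | 0.071 | 0.080 |
| 25% | 0.813 | 0.216 | 0.234 |
| 50% | 0.875 | 0.703 | 0.721 |

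In patients, f = 10% at n = 58 is 58 × 0.25 × 0.10 = 1.45 expected conversions, and f = 25% is 3.6.

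**The case against.** A reader might infer that the plan does count bronchoscope rescues as device successes and that the primary rate is therefore inflated. The documents do not support that. No sentence says that these cases enter the numerator, and none reports that a bronchoscope was used in any patient.

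The wording also narrows the gap. The endpoint carries a first-attempt condition, and the number of intubation attempts is analysed. A bronchoscope brought in after a failed pass would naturally be a second attempt and already a non-success. The list of adjustments is triggered by mask position and precedes tube advancement, and the video-guidance sentence suggests that the mask's camera was the intended route. These points stand. What remains open is a bronchoscope used on the first pass: video guidance describes the procedure but is not one of the success criteria.

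It is also tempting to say that two patients can overturn the result. At n = 58 that holds only for an observed 50 or 51 successes; from 52/58 it takes three. Nor is this the trial's only hypothesis test, since correlation analyses at p < 0.05 are planned too. It is the only test specified for the primary success rate.

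Finally, success with the device alone and success with permitted adjuncts are both legitimate quantities. The counting rule behind the 0.75 benchmark lies in a cited source and is not in the documents, so a stricter rule could reduce comparability. This is a fair objection, and it is why both counts should be reported.

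**Conclusion.** The concern holds as a gap in the endpoint definition: applied literally, the stated criterion lets a first pass guided by a second visual device count as a SaCoVLM success. Any bias in the device-alone rate is upward. Its size cannot be computed from the documents, and it is zero if no bronchoscope was used on a first pass.

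The result is sensitive to small numbers. Three recoded cases are enough from an observed 90%. On the assumption that unaided success is 0.75, converting 10% of failures takes the type I error above the nominal 0.05 at either enrolment figure. At 5% it stays below 0.05 with 58 patients and slightly exceeds it with 57. These figures rest on assumed conversion shares and show sensitivity, not what happened.

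This should be fixed. It is not a demonstrated bias, and assisted cases can be separated if the optimization used was recorded patient by patient.

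**What to change.** Define an attempt as one tube pass. Define primary success as intubation on the first tube pass under SaCoVLM video guidance, with bronchoscope-guided passes coded as non-success for this device-alone endpoint. Mask manoeuvres made before the first pass may still count as success.

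As a secondary or sensitivity result, report the rate and the exact test with bronchoscope-assisted first passes counted as successes. State which of the two counts matches the rule behind the 0.75 benchmark. Reconcile the enrolment figures of 57 and 58 so that the denominator and rejection limit are fixed.

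The cost is wording and recoding. The primary rate may be slightly lower, and the power calculation should say whether the assumed 0.90 includes assisted cases. The recoding is possible only if the optimization used was recorded for each patient; its listing as a secondary endpoint suggests this but does not confirm it. Clinical use of the manoeuvres is not affected.

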Figure 1. SaCoVLM video intubation laryngeal mask airway. Photo courtesy of Zhejiang UE Medical Corp. (Hangzhou, China).

Figure 2. Trial flow chart.

Figure 3. Glottic exposure grades. (Based on the suggestions of Timmermann A et. al.)

Figure 4. Association of intubation time with study outcomes: (A) BMI, (B) thyromental distance, (C) mouth opening, (D) neck circumference, (E) Mallampati classification, (F) OSA classification.
